6.2.2 Secondary analyses

The secondary analysis will be done according to the FAS (ITT) and PP sets specified in section 4.2. Models will also be adjusted for the stratification factor and relevant covariates, with bootstrapped standard errors, as described for the primary analysis. Effects will be shown using marginal point estimates (accounting for adjustment variables) and 95% confidence intervals.

For the first secondary endpoint, AEs and SAEs, we will use a Cox regression, e.g.:

stset timevar, failure(y) id(idvar)

bootstrap, reps(1000) seed(XXX): stcox x1 x2

We will use multiple imputation to handle missing values on covariates (see section 6.4). There won't be missing values on (S)AEs, as participants who drop out from the study will be right-censored. If there is collinearity between covariates, we will remove one colinear variable based on theoretical reasons. If the assumption of proportionality of hazard is not met, we will stratify on the problematic variable(s).

For the second secondary endpoint, *proportion of PCP who agree to participate*, we will calculate a percentage with a 95% confidence interval, using Wilson intervals which are superior for small samples without being overly conservative like exact methods (6), e.g.:

cci proportions n x, Wilson

For analyses on the PP set, we will run the same analyses as described in section 6.2.1. In addition, we will use inverse probability weighting for ICE1 and ICE2. We will derive stabilized weights separately and combined them by multiplying them. The covariates used to create weights are the following. For ICE1, we will use for GP/walk-in clinic, age, sex, education, beginning of symptoms (number of days), and baseline ABSS. For ICE2, we will use for GP/walk-in clinic. We will runcate weights at

SAP for PHYTOBRONCH	Version of SAP: 1	
Based on template: CTU_STA_TEM-11; v5.0.0	Valid from: 20.03.2025	Page 13 of 15

the 99th percentile. The weights will then be used in the main adjusted model to re-balance randomization groups. We will check whether balance was achieved using standardized mean/proportion differences, which should be lower than .25 (7, 8). As balance may not be achieved using multiple imputation, we will use simple imputation in models using inverse probability weighting.

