4.2.2 Per-protocol (PP)

Per-protocol (PP) analyses will be conducted in participants who do not have any intercurrent events (ICEs). ICEs include:

- ICE1: Non-respect of the treatment strategy, including cross-over (use phytotherapy in the control group or not used Kaloba® in the intervention group), non-adherence to treatment (adherence is defined as missing the treatment at least 50% over the period of symptoms (and maximum for 7 days), use of antibiotics at baseline, use medications other than those authorized (exclusion criteria 12, section 5.2), discontinuation of treatment in the intervention group (e.g., due to AEs or lack of efficacy), already using Kaloba® or Umckaloabo® in the control group (exclusion criteria 11, section 5.2).
- ICE2: Inclusion despite presence of an exclusion criterion (criteria 1 to 10, section 5.2) or lack of an inclusion criterion (criteria 1 to 3, section 5.2).
- ICE3: Terminal events, such as death.

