Handling of intercurrent events: All participants are included. Participants who took antibiotics at baseline will be considered as failures (having antibiotics).

Handling of missing data: Missing data will be multiple imputed (see section 6.4).

* Same adjustment as E1.1. If there are too few participants, we will use analyses adjusting separately for each covariate + type of recruitment.

Estimand E2.2: This estimand quantifies the efficacy of the treatment assessed with the proportion of antibiotics use (co-primary outcome) in the PP population.

Outcome of interest: same as estimand 2.1.

Population-level summary measure of outcome: same as estimand 2.1.

Participant-set of interest: PP.

Handling of intercurrent events: Participants with ICE1-3 are excluded from the analysis. The data will be weighted according to inverse probability weighting for ICE 1 and 2 (see section 6.2.2).

Handling of missing data: As ICE cannot be assessed in participants who drop out or are lost to follow-up, we will not use multiple imputation. We will use inverse probability of attrition weights to account for attrition and multiple imputation for missing baseline covariates (see section 6.4).

Estimand E3.1: This estimand quantifies the incidence of AEs and SAEs.

Outcome of interest: Presence of any adverse or severe adverse event (binary) during the follow-up (up to 22 days).

Population-level summary measure of outcome: adjusted^{*} hazard ratio.

Participant-set of interest: SAF.

Handling of intercurrent events: All participants are included.

Handling of missing data: No missing data, participants are censored when the study ends (at day 22) or at the day of last contact.

* 1) Adjusted for the type of recruitment (PCP/walk-in clinic) and 2) adjusted for the following factors at baseline: type of recruitment, age, sex, level of education, smoking status, beginning of symptoms (number of days), and baseline ABSS. If there are too few participants, we will use analyses adjusting separately for each covariate + type of recruitment.

Estimand E3.2: This estimand quantifies the incidence of AEs and SAEs.

Outcome of interest: same as estimand 3.1.

Population-level summary measure of outcome: same as estimand 3.1.

Participant-set of interest: SAF without ICE2.

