Handling of intercurrent events: Participants with ICE2 are excluded from the analysis. The data will be weighted according to inverse probability weighting for ICE 2 (see section 6.2.2). Participants will be censored when they deviate from the treatment strategy (ICE1) and when they have a terminal event (ICE3).

Handling of missing data: No missing data, participants are censored when the study ends (at day 22) or at the day of last contact.

SAP for PHYTOBRONCH	Version of SAP: 1	
Based on template: CTU_STA_TEM-11; v5.0.0	Valid from: 20.03.2025	Page 9 of 15

Estimand E4: This estimand quantifies the proportion of PCPs who agree to participate in the study.

Outcome of interest: PCP agrees or declines to participate in the study (binary).

Population-level summary measure of outcome: Percentage.

Participant-set of interest: FAS PCPs.

Handling of intercurrent events: All PCPs are included.

Handling of missing data: No missing data (missing data are considered as refusal to participate in the study).

SAP for PHYTOBRONCH	Version of SAP: 1	
Based on template: CTU_STA_TEM-11; v5.0.0	Valid from: 20.03.2025	Page 10 of 15

5. Trial Population

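### SAP 6.2.2 places adverse events on the FAS and PP sets, against the SAF estimands in 4.3, and its PP run would favour Kaloba

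*Combined protocol and SAP*

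**What the plan says.** SAP section 6.2.2 opens with the sets for all secondary endpoints: "The secondary analysis will be done according to the FAS (ITT) and PP sets specified in section 4.2". The AE method comes under that sentence: "For the first secondary endpoint, AEs and SAEs, we will use a Cox regression, e.g". The SAF is not named in 6.2.2, and section 6.5 (safety evaluation) only refers the reader back there.

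Section 4.3 assigns the same endpoint differently.

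- E3.1: "Participant-set of interest: SAF", with "Handling of intercurrent events: All participants are included".
- E3.2: "Participant-set of interest: SAF without ICE2". Here "Participants with ICE2 are excluded from the analysis", with weighting for ICE2, and "Participants will be censored when they deviate from the treatment strategy (ICE1) and when they have a terminal event (ICE3".

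Section 4.2.2 limits the PP set to participants with no intercurrent event of any type. One component of ICE1 is "discontinuation of treatment in the intervention group (e.g., due to AEs or lack of efficacy".

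**The concern.** The section that describes the analysis and the section that defines the estimands give different populations and different handling of ICE1 for the first secondary endpoint. An analyst who programs from 6.2.2 would run AEs on the FAS and PP sets. One who programs from 4.3 would run them on the SAF and on the SAF without ICE2. The independent code check in section 6.8 covers sections 6.2.1 to 6.2.4, so it would be made against the conflicting text.

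The PP set is a poor place for AEs because part of its definition depends on the outcome. A Kaloba participant who stops because of an AE leaves the set and takes the event along. A PP comparison of AEs would therefore understate the AE rate on Kaloba.

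**Working it through.** **1. The sections side by side**

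| | E3.1 (4.3) | E3.2 (4.3) | 6.2.2, FAS run | 6.2.2, PP run |
|---|---|---|---|---|
| Set | SAF | SAF without ICE2 | All randomized | No ICE of any type |
| ICE1 | Kept | Censored at the event | Kept | Excluded |
| ICE2 | Kept | Excluded | Kept | Excluded |
| ICE3 | Kept | Censored at the event | Kept | Excluded |
| Weights | None | ICE2 only | None | ICE1 × ICE2 |

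The FAS run differs from E3.1 only by randomized participants who took no medication. Usual care is not standardized (section 2.1), so that gap could be uneven between arms, but nothing suggests it is large. The PP run differs from E3.2 in the set, in the handling of ICE1 and ICE3, and in the weights.

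**2. Can the weights repair the PP run?** Section 6.2.2 builds the ICE1 weights from site type, age, sex, education, days since symptom onset and baseline ABSS. Two Kaloba participants with the same values on these get the same weight whether or not they had an AE. The weights can make the retained participants resemble the full arm at baseline. They cannot replace people removed because of something that happened on study.

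**3. Size of the distortion.** The documents state no AE rate, no AE-related stopping rate and no power for this endpoint, so there is no planned figure to reproduce. Everything below is assumed. Let *a* be the true AE risk in both arms and *s* the share of Kaloba participants with an AE who stop because of it. Only those participants are removed, and no weights are applied.

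- Kaloba PP risk = *a*(1 − *s*) / (1 − *as*)
- PP risk ratio = (1 − *s*) / (1 − *as*), where the truth is 1

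With *a* = 0.15:

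| *s* | Kaloba PP risk | PP risk ratio |
|---|---|---|
| 0.20 | 0.120 / 0.970 = 12.4% | 0.82 |
| 0.30 | 0.105 / 0.955 = 11.0% | 0.73 |
| 0.50 | 0.075 / 0.925 = 8.1% | 0.54 |

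Varying *a* from 0.10 to 0.30 changes little:

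- *s* = 0.20: 0.8/0.98 = 0.82 to 0.8/0.94 = 0.85
- *s* = 0.30: 0.7/0.97 = 0.72 to 0.7/0.91 = 0.77
- *s* = 0.50: 0.5/0.95 = 0.53 to 0.5/0.85 = 0.59

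**4. On the hazard-ratio scale.** The planned measure is a hazard ratio, approximated here as ln(1 − Kaloba risk) / ln(1 − control risk). With a true risk of 20% in both arms and *s* = 0.10, 0.25 or 0.50, the Kaloba PP risk is 18.4%, 15.8% or 11.1%. A true hazard ratio of 1.00 then appears as about 0.91, 0.77 or 0.53. With a true excess of 30% against 20%, the true ratio is ln(0.70)/ln(0.80) = 1.60, and the PP run would show about 1.46, 1.25 or 0.87.

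**The case against.** The best defence is that the intended analysis is already in the SAP. Section 4.2.3 defines the SAF, E3.1 and E3.2 assign AEs to it, and no estimand places AEs on the PP set. E3.2 itself points to 6.2.2 for its weighting, so the sections were meant to be read together. The opening of 6.2.2 nearly repeats that of 6.2.1 and looks carried over. Read literally it would also cover PCP participation, for which no PP set is defined. The PP paragraph of 6.2.2 refers to the analyses of 6.2.1, which contains only the co-primary models. All of this stands as an account of how the sentence probably arose. It does not remove the conflict, because 6.2.2 is the operative methods text and nothing gives 4.3 precedence.

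A reader might infer that the SAP has no SAF analysis. That is true of 6.2.2 alone, not of the plan. A reader might also infer that following 6.2.2 would bias the safety comparison as a whole. The documents do not support this. Section 6.2.2 names the FAS as well, the FAS keeps participants who discontinue, and the mechanism is absent there. A biased PP result would stand beside an FAS result without this bias. E3.2, for its part, censors at ICE1, so an AE before the stop still counts.

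Finally, other ICE1 components, such as cross-over to phytotherapy, can remove control participants, and the illustration ignores these. None of them is defined by an AE, so they do not offset the mechanism by design, but the figures are not estimates for this trial.

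**Conclusion.** The point holds as an internal contradiction with one consequential part. Section 6.2.2 and section 4.3 prescribe different populations for AEs and SAEs, and the text must be reconciled. The FAS/SAF mismatch is minor. A PP analysis of AEs would be biased in favour of Kaloba: the direction follows from the ICE1 definition, provided some Kaloba participants stop because of an AE. The size depends on rates that the documents do not give. A PP risk ratio of about 0.82 to 0.54 under no true difference rests on an assumed 15% AE risk in both arms, 20% to 50% AE-related stopping among those with an AE, and no AE-related removals from the control arm. It is worth correcting because AEs and SAEs are the first secondary endpoint and the correction is free.

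**What to change.** Replace the opening sentence of section 6.2.2 with wording such as:

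> AEs and SAEs are analysed in the SAF (E3.1) and in the SAF without ICE2, weighted for ICE2 only and censored at ICE1 and ICE3 (E3.2). No AE analysis uses the PP set. PCP participation uses the FAS of PCPs (E4).

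In the PP paragraph of 6.2.2, state that the combined ICE1 and ICE2 weights apply only to the co-primary PP analyses (E1.2 and E2.2). Without this, it stays unclear which weights E3.2 uses. In the same edit the sponsor could say how an AE on the day of ICE1 censoring is ordered, which the SAP leaves open.

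The cost is SAP wording before database lock. No new data, visits or participants are needed, and the analysis sets are those that section 4.3 already defines.

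### The per-protocol weight models name neither randomised group nor fitting by arm, so as listed they cannot re-balance the arms when ICE1 selection differs between them

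*Combined protocol and SAP*

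**What the plan says.** SAP section 4.3 (estimands E1.2 and E2.2) excludes participants with an intercurrent event from the per-protocol (PP) set and handles ICE1 and ICE2 by inverse probability weighting. Section 6.2.1 names the PP set beside the FAS within the primary analysis.

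Section 6.2.2 gives the weight covariates. For ICE1: "For ICE1, we will use for GP/walk-in clinic, age, sex, education, beginning of symptoms (number of days), and baseline ABSS". For ICE2: "For ICE2, we will use for GP/walk-in clinic". Randomised group is in neither list. On construction it says: "We will derive stabilized weights separately and combined them by multiplying them". On purpose: "The weights will then be used in the main adjusted model to re-balance randomization groups". On the check: "We will check whether balance was achieved using standardized mean/proportion differences, which should be lower than .25 (7, 8".

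Section 4.2.2 defines several parts of ICE1 by arm. Cross-over is "cross-over (use phytotherapy in the control group or not used Kaloba® in the intervention group". One component is for the intervention arm only: "discontinuation of treatment in the intervention group (e.g., due to AEs or lack of efficacy". Another is for controls only: "already using Kaloba® or Umckaloabo® in the control group". Antibiotics at baseline and unauthorised medication apply to both arms.

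Section 6.4 adds attrition weights that are multiplied in, with no covariate list of their own and no mention of group.

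**The concern.** Being free of ICE1 means something different in each arm, so its frequency and its relation to illness severity may well differ by arm. If so, the PP exclusions break the balance that randomisation gave, and the weights are there to restore it. A model without group gives the same weight to an intervention and a control participant with the same covariates, so it cannot undo a selection that differs between arms.

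At stake are E1.2 and E2.2. The report would describe weighted PP analyses while the weights left the between-arm imbalance in place. Protection against selective adherence would then rest on the outcome regression alone.

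**Working it through.** **The plan's own figures.** The SAP gives no figure for the weights. Its sample size supplies the trial size and SD used below, and it reproduces. Antibiotics: n per arm = [z(0.9875)·√(2p̄q̄) + z(0.80)·√(p₁q₁+p₂q₂)]² / (p₁−p₂)², with 60% v 45% and p̄ = 0.525. This is [2.241×0.706 + 0.842×0.698]² / 0.0225 = 209.4, so 210 per arm and 420 in total, as stated. Symptoms: difference 1 day, SD 3 days, t-based: 173 per arm and 346 in total, as stated.

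**Reading of the construction sentence.** The weights derived separately are then multiplied. Two weights can be multiplied only within one participant, so the sentence means separately for ICE1 and ICE2, not separately by arm.

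**Algebra.** Let f(x) be the covariate distribution at randomisation (the same in both arms), q_a(x) the probability of being ICE1-free in arm a, and Q_a its average.
- Unweighted PP set: the distribution of x in arm a is proportional to f(x)·q_a(x). The intervention-to-control ratio at x is proportional to q₁(x)/q₀(x).
- Weights as listed, w(x) = Q/q(x): the distribution is proportional to f(x)·q_a(x)/q(x). The factor 1/q(x) cancels, so the ratio is still proportional to q₁(x)/q₀(x).
- Weights by arm, w_a(x) = Q_a/q_a(x): the distribution is proportional to f(x) in both arms, so balance is restored.

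Putting group only in the stabilising numerator rescales each arm by a constant and leaves its weighted mean of x unchanged. Group has to enter the denominator model.

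**Size.** ICE1 rates and their dependence on severity are not in the documents, so these are assumptions. Set-up: one standardised covariate x; no treatment effect; outcome SD 3 days, with x worth 1 day per SD; stabilised weights truncated at the 99th percentile. Rates and slopes (log-odds of ICE1 per SD of x) are intervention/control. Standardised differences in x are from N = 400,000. The last column is from 400 simulated trials of 420, using the weights as listed.

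| ICE1 rates | Slopes | Unweighted | As listed | Group as main effect | By arm | Trials beyond 0.25 |
|---|---|---|---|---|---|---|
| 20%/20% | 0.5/0.5 | 0.00 | 0.00 | 0.00 | 0.00 | not run |
| 30%/10% | 0.5/0.5 | -0.09 | -0.09 | 0.00 | -0.01 | not run |
| 30%/10% | 0.5/0 | -0.15 | -0.15 | -0.09 | -0.01 | 18% |
| 30%/10% | 1/0 | -0.26 | -0.28 | -0.18 | -0.03 | 60% |
| 30%/10% | 1/-0.5 | -0.32 | -0.33 | -0.25 | -0.04 | 76% |
| 40%/10% | 1/-1 | -0.45 | -0.46 | -0.37 | -0.05 | 96% |

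In no scenario did the weights as listed reduce an imbalance. Group as a main effect suffices only when the slopes are equal. The small remainder by arm comes mainly from truncation.

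**Effect on the estimate.** Where slopes differ, the difference weighted as listed but not covariate-adjusted is biased by about -0.14 to -0.44 days, against a 1-day design difference. After adjusting for x in a correct linear model, the bias is within about 0.02 days. With assumed quadratic or effect-modification terms left out of the model, the adjusted bias was about 0.01 to 0.09 days with weights as listed and 0.00 to 0.04 days by arm. In a log-link model with a true risk ratio of 1, the adjusted risk ratio was 1.007 as listed and 1.004 by arm; without adjustment it was 0.94 and 1.00.

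**The case against.** **The list may be silent without meaning to exclude group.** The SAP treats group as the predictor and covariates as a separate matter, and its adjustment and imputation lists omit group too. A reader might infer that the sponsor chose a model pooled over arms; the text does not show that. It does show that nothing says the models include group or are fitted by arm, and that the list followed literally cannot serve the stated purpose.

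**The outcome model already adjusts.** This is the strongest objection, and it stands. The weights enter the main adjusted model, and the E1.1 list, which E1.2 takes over, contains all six ICE1 weight covariates. A reader might infer a seriously biased PP result; the calculations do not support that where this model is correct. Two limits remain. The model may be misspecified. And for antibiotics, section 4.3 allows a fallback with one covariate at a time plus type of recruitment, which leaves the other covariates to the weights.

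**The balance check would catch it.** In part. A reader might infer that the 0.25 limit is blind to the problem. It is not: it looks at the right quantity and flags strong selection in most trials (60% to 96% in the last three rows). It is lenient: in the 30%/10%, 0.5/0 scenario it passes 82% of trials.

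**Selection may not differ by arm.** Some ICE1 components apply to both arms, and with equal rates and slopes there is no imbalance to correct. That is possible, but the arm-specific definitions make it an unsafe assumption. For ICE2 the objection is stronger: eligibility is fixed before randomisation, so a difference by arm is less likely.

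**Conclusion.** The point holds as a defect of specification. Weights built from the listed covariates alone cannot re-balance the PP arms when ICE1 selection differs by arm. That follows from algebra; only its size depends on the assumed rates and slopes, for which the documents give no values. Across those assumptions the uncorrected standardised difference runs from 0.00 to -0.46, against 0.00 to -0.05 with weights fitted by arm.

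The practical harm is modest. Bias is close to zero where the outcome model adjusts correctly for all six covariates, and was at most about 0.09 days under the misspecifications tried. What is lost is the second safeguard, which matters more under misspecification or the one-covariate-at-a-time fallback for antibiotics. The FAS estimands E1.1 and E2.1 are untouched.

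No form of these baseline weights deals with post-baseline drivers of ICE1, such as the adverse events and lack of efficacy that section 4.2.2 itself names.

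**What to change.** In section 6.2.2, state that the ICE1 and ICE2 weight models are fitted separately in each randomised group (or with group and group-by-covariate terms), with the group-specific probability of being free of the event as the stabilising numerator. Group as a main effect alone is not enough. Apply the same rule to the attrition weights in section 6.4 and list their covariates there.

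The cost is a sentence or two in each section and a few lines of code. The downside is sparse data. If 10% of 210 controls had ICE1, that is 21 events; at 5% it is about 10. The six covariates need seven coefficients, because education has three levels, so there would be 21/7 = 3 events per coefficient or fewer. The SAP should therefore allow a reduced or penalised covariate set in an arm with few events.

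Do not replace the 0.25 limit with a 0.10 pass/fail rule. With by-arm weights, 32% to 40% of simulated trials of 420 still exceeded 0.10 on a single covariate by chance. Reporting the weighted standardised differences for inspection is enough.

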4.3 Estimands

We define the following estimands for the outcomes.

Estimand E1.1: This estimand quantifies the effectiveness of the treatment assessed with the reduction of symptom severity (co-primary outcome).

Outcome of interest: Number of days needed to achieve a 50% reduction on the Acute Bronchitis Severity Score (ABSS) after peak of symptoms, assessed at max. 22 days. The peak of symptoms is defined by the highest ABSS (or the initial score if there is no peak). This is a normally distributed count outcome (3).

Population-level summary measure of outcome: adjusted* mean difference.

Participant-set of interest: FAS.

Handling of intercurrent events: All participants are included.

Handling of missing data: Missing data will be multiple imputed (see section 6.4).

* 1) Adjusted for the type of recruitment (PCP/walk-in clinic) and 2) adjusted for the following factors at baseline: type of recruitment, age, sex, level of education, smoking status, beginning of symptoms (number of days), baseline ABSS, and prescriptions for corticosteroid containing oral medication or inhalers (yes/no), including Prednisone, Symbicort, and Vannair.

Estimand E1.2: This estimand quantifies the effectiveness of the treatment assessed with the reduction of symptom severity (co-primary outcome) in the PP population.

Outcome of interest: Same as estimand 1.1.

Population-level summary measure of outcome: same as estimand 1.1.

Participant-set of interest: PP.

Handling of intercurrent events: Participants with ICE1-3 are excluded from the analysis. The data will be weighted according to inverse probability weighting for ICE 1 and 2 (see section 6.2.2).

Handling of missing data: As ICE cannot be assessed in participants who drop out or are lost to follow-up, we will not use multiple imputation. We will use inverse probability of attrition weights to account for attrition and multiple imputation for missing baseline covariates (see section 6.4).

SAP for PHYTOBRONCH	Version of SAP: 1	
Based on template: CTU_STA_TEM-11; v5.0.0	Valid from: 20.03.2025	Page 8 of 15

Estimand E2.1: This estimand quantifies the efficacy of the treatment assessed with the proportion of antibiotics use (co-primary outcome).

Outcome of interest: Use of antibiotics after the initial visit (binary).

Population-level summary measure of outcome: adjusted* risk ratio.

Participant-set of interest: FAS.

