6.2 Analysis methods

6.2.1 Primary analysis

The primary analysis will be done according to the FAS (ITT) and PP sets specified in section 4.2, using the adjusted model (4, 5). The randomization group will be used as the main predictor, adjusting for the stratification factors and relevant predefined covariates. To account for the fact that participants are clustered in PCP practices, we will use bootstrapped standard errors (1000 reps). A random seed will be predefined for replicability. The intraclass coefficient is expected to be small. All effects will be shown using marginal point estimates (accounting for adjustment variables) and 95% confidence intervals.

For the first co-primary endpoint, reduction in ABSS, we will use a linear regression, e.g.:

bootstrap, reps(1000) seed(XXX): regress y x1 x2

This endpoint should be normally distributed, as observed in previous studies (3). However, if it is not normally distributed, we will use a log-transformation after adding the constant 1.

For the second co-primary endpoint, *proportion of antibiotics use*, we will use a logistic regression, e.g.:

bootstrap, reps(1000) seed(xxx): glm y x1 x2, fam(bin) link(log) eform

We will use multiple imputation to handle missing values on covariates and outcomes (see section 6.4). If there is collinearity between covariates, we will remove one collinear variable based on theoretical reasons.

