6.4 Missing data

For missing data on outcomes and covariates, we use multiple imputation by chained equations (MICE), under the assumption of missing at random (MAR). Ten imputation datasets will be created

SAP for PHYTOBRONCH	Version of SAP: 1	
Based on template: CTU_STA_TEM-11; v5.0.0	Valid from: 20.03.2025	Page 14 of 15

and results pooled using Rubin's rule. The following auxiliary variables will be used to predict missingness: type of recruitment (PCP/walk-in clinic), age, sex, level of education, smoking status, beginning of symptoms (number of days), and baseline ABSS. Variables with missing values will be removed from the auxiliary list of variables. Terminal events such as death will be used as auxiliary variables. Technical issues (e.g., wrong email, reminder not sent) that cause missingness will also be used as auxiliary variables. For the PP analyses, we will also use inverse probability of attrition weights, which will be combined to inverse probability weights accounting for ICEs by a multiplication. We will use stabilized weights, truncated at the 99th percentile.

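### The per-protocol weights for ICE1 use baseline variables only, so they cannot correct exclusions driven by symptom course after randomisation; the net direction of the bias is not known in advance

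*Combined protocol and SAP*

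**What the plan says.** SAP section 4.2.2 defines ICE1 broadly. Some components are settled at or near baseline: antibiotics at baseline, already using the product, never taking it. Others arise during follow-up. One of these applies to the Kaloba arm only: "discontinuation of treatment in the intervention group (e.g., due to AEs or lack of efficacy". Another can remove participants from either arm: "cross-over (use phytotherapy in the control group or not used Kaloba® in the intervention group". Unauthorised medication and non-adherence are also listed.

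For E1.2 and E2.2, section 4.3 states "Participants with ICE1-3 are excluded from the analysis" and then "The data will be weighted according to inverse probability weighting for ICE 1 and 2". Section 6.2.2 gives the ICE1 weight covariates: "For ICE1, we will use for GP/walk-in clinic, age, sex, education, beginning of symptoms (number of days), and baseline ABSS". It describes their use as follows: "The weights will then be used in the main adjusted model to re-balance randomization groups". Balance is to be judged by standardised differences below .25, with no variables named.

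Section 6.4 adds, "For the PP analyses, we will also use inverse probability of attrition weights", and names no symptom or adverse-event predictor measured after baseline. On the role of the PP set, section 6.2.1 says "The primary analysis will be done according to the FAS (ITT) and PP sets specified in section 4.2".

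**The concern.** Inverse probability weights remove selection only through the variables in the weight model. Take two Kaloba participants with the same recruitment site type, age, sex, education, symptom duration and baseline ABSS. One improves by day 4 and continues; the other does not and stops. Both have the same modelled probability of remaining in the PP set. The one who stops is removed, and nobody with a similarly poor early course is weighted up to stand in.

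At stake is how E1.2 and E2.2 are read. They would be reported as weighted for treatment deviation, next to the FAS results, while the deviation most closely tied to outcome had hardly been addressed. The trial is open-label (section 2.8), so stopping or switching in response to perceived benefit is plausible in both arms.

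**Working it through.** **1. Does anything else in the SAP correct this?**

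- The outcome model (section 4.3) adjusts for baseline factors only.
- The attrition weights (section 6.4) address drop-out and name no post-baseline symptom or adverse-event covariate.
- The balance check (section 6.2.2), if applied to baseline covariates, could pass with this selection fully present.
- The sensitivity analyses (section 6.2.3) concern only the distribution of the endpoint.

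None of these reaches selection on later symptom course.

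**2. Design figures (section 2.3), as scale.** Difference 1 day, SD 3 days, two-sided 2.5%, power 80%: the noncentral-t calculation gives 173 per arm, 346 in total, as stated. For 60% v 45%, the pooled test without continuity correction gives 210 per arm, 420 in total, as stated. With 210 per arm, the standard error of the mean difference is 3 × √(2/210) = 0.29 day.

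**3. Simulation with no true effect.** The SD is the SAP's 3 days. The following are assumptions, because the documents do not give them: stopping rates, an odds ratio for stopping of 2 to 4 per SD of early (day-4) severity, a correlation of 0.6 between early severity and outcome, and 0.3 between baseline and early severity. There were 200,000 participants per scenario. Stabilised weights were fitted within arm and truncated at the 99th percentile. The Monte Carlo standard error is roughly 3 × √(4/200,000) = 0.013 day. Negative values favour Kaloba.

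| Removed: Kaloba / control | Unweighted (days) | Baseline-only weights (days) | Early severity added (days) |
|---|---|---|---|
| 5% / 0% | -0.05 to -0.11 | -0.05 to -0.11 | -0.02 to 0.00 |
| 10% / 0% | -0.09 to -0.19 | -0.09 to -0.19 | -0.02 to +0.01 |
| 20% / 0% | -0.23 to -0.35 | -0.23 to -0.36 | -0.04 to -0.03 |
| 30% / 0% | -0.30 to -0.53 | -0.30 to -0.53 | -0.07 to -0.01 |
| 10% / 10% | -0.02 to +0.02 | -0.02 to +0.02 | -0.02 to +0.02 |
| 20% / 10% | -0.09 to -0.14 | -0.09 to -0.15 | +0.01 |
| 10% / 20% | +0.11 to +0.16 | +0.11 to +0.16 | 0.00 to +0.01 |

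Baseline-only weights change almost nothing. Stopping unrelated to severity, as with an adverse event that has no link to outcome, gave +0.01 day at 20%: no bias.

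**4. Analytic check of one cell.** Let π(x) be the stopping probability at early severity x (standard normal) and p its mean. Those who stay have mean severity ∫x(1 − π(x))φ(x)dx / (1 − p). At p = 20% and odds ratio 4 this is -0.216 SD. The bias after baseline adjustment is about 3 × 0.6 × (-0.216) × (1 − 0.3²) = -0.35 day, which agrees with the simulated -0.36.

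**5. Sensitivity to the assumed correlation (removal in the Kaloba arm only).** At 0.4, with odds ratios 2 to 3, the bias is -0.06 to -0.11 day at 10% and -0.14 to -0.21 at 20%. In a separate simulation (correlation 0.72, SD 2.9 days, logistic slope 0.35 per ABSS point) it is -0.21 day at 10%, -0.31 at 16% and -0.44 at 24%. The midpoint of the last two is (-0.31 − 0.44)/2 = -0.375 at 20%. Together these give about -0.05 to -0.2 day at 10% and -0.15 to -0.4 at 20%.

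**6. Antibiotic use (E2.2).** In the simulation of step 3, with an assumed event rate near 50% and removal in the Kaloba arm only, the risk ratio under no effect with baseline-only weights is 0.979 to 0.987 at 10%, 0.950 to 0.967 at 20%, and 0.926 at its lowest (30%, odds ratio 4).

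**The case against.** A reader might infer that the PP analysis is bound to favour Kaloba. The documents do not support that. Section 4.2.2 also removes controls who take phytotherapy and participants in either arm who take unauthorised medication. In an open-label trial, controls doing badly may well be the ones who cross over. The 10% / 10% and 10% / 20% rows show the bias vanishing or reversing. Stopping for adverse events cannot be counted with lack of efficacy unless it is related to outcome. This objection stands in full.

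The size is also open to challenge. The stopping rates and correlations are assumed. The endpoint in section 6.1 counts days from each participant's own peak, so a high day-4 score may mark a late peak rather than slow recovery, which weakens the correlation. At 10% stopping the bias is less than one standard error (0.19/0.29 = 0.66 at the top of the main range). This stands as a reason to give ranges, not as a reason to leave the weights as they are.

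A reader might also infer that the main trial result is compromised, because section 6.2.1 names the PP set within the primary analysis. It is not: E1.1 and E2.1 use the FAS with everyone included.

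Finally, section 6.2.2 says only that the weights re-balance the groups. But section 4.3 offers weighting for ICE1 as the handling of the excluded participants, and post-randomisation stopping is part of ICE1. This part of the objection does not remove the point.

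**Conclusion.** The point holds for E1.2 and E2.2. The ICE1 weights omit every measure of response after randomisation although ICE1 includes stopping for lack of response, and nothing else in the SAP makes up for it. The lack-of-efficacy component on its own pushes towards Kaloba. The sign for ICE1 as a whole depends on outcome-related removals in both arms, for which the documents give no rates.

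For removal in the Kaloba arm only, the ranges in step 5 amount to at most about a fifth of the design difference at 10% stopping and two fifths at 20%. At 5% or less the bias is small. These sizes rest on the assumed links between early severity, stopping and outcome. That baseline-only weights barely help was seen under every set of assumptions in which stopping depended on early severity and removal was unequal between arms. The change should be made, but the FAS conclusions do not depend on it.

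**What to change.** In section 6.2.2, split ICE1 by timing.

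- **Fixed at or near baseline** (antibiotics at baseline, already using Kaloba, never starting it): keep the baseline-only weight model.
- **Arising during follow-up** (discontinuation, cross-over, unauthorised medication, non-adherence): estimate the probability of remaining free of the event within arm, over intervals, for example to day 4 and to day 8. Use the listed covariates plus the most recent ABSS before the deviation, its change from baseline, and any prior adverse event. Non-adherence is a cumulative threshold, so state the interval to which it is assigned.
- **Missed diary days**: use the last available diary or phone ABSS, or the single imputation already planned for weighted models.
- **Combining**: multiply over intervals and truncate at the 99th percentile as planned. Keep the post-randomisation variables out of the outcome model.

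Add a sentence that the PP results still assume no unmeasured selection and are supportive of the FAS.

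The cost is more programming and somewhat more variable weights. Daily ABSS and adverse-event dates are already collected (section 6.1). E3.2 already censors at the ICE1 deviation, so a deviation date is presupposed. The SAP does not describe how Kaloba stop dates are recorded, and this should be confirmed before the model is fixed. If the dates prove unusable, the minimum is to state the assumption and label the PP results as supportive.
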